#### **6.7.5.2. QoL-B** (Adults only)

QoL-B will be completed every 14 days. Windowing will be performed as given in Table 6. In case of multiple QoL-B assessments falling into an interval, the observation closest to the target study day will be selected; or the latter observation if 2 (or more) observations are equally close to the target study day.

Calculation of QoL-B domain scores is detailed in Appendix A.

#### 6.7.5.3. Bronchiectasis Exacerbation and Symptoms Tool (Adults only)

The BEST Diary will be completed every day and a score will be calculated for each daily entry. BEST Diary Baseline Score is defined as average of BEST Diary daily scores from screening to Study Day 1 (inclusive). The daily change from Baseline in BEST score over the 52-week treatment period will be calculated for each participant as the individual daily change from baseline. In addition, a BEST Diary Score (overall post-baseline) will be calculated, defined as the average of all the non-missing BEST Diary daily score for a given participant post-baseline.

BEST data will also be averaged over 4-week periods in a table and figure.

Calculation of the BEST score is detailed in Appendix E.

#### 6.7.5.4. Patient Global Impression of Severity scale (PGI-S) in Adults

PGI-S will be completed every 14 days. Adult participants enrolled under global CSP amendment 2 and later will complete the PGI-S on an electronic device where validated translations are available in the local language. Participants enrolled prior to global CSP amendment 2 will not complete the PGI-S.

The PGI-S assesses how a participant perceives their overall severity over the past week. The response options of the PGI-S are scored using a 5-point scale: 0 = None; 1 = Mild; 2 = Moderate; 3 = Severe; 4 = Very Severe. Negative change from baseline indicates improvement (post therapy score – baseline score < 0).

No additional scoring will be performed for the PGI-S. If PGI-S was assessed more than once within 2 weeks, the observation closest to the target Study Day will be selected; or the latter observation if 2 observations are equally close to the target Study Day. All data will be listed.

CONFIDENTIAL Page 44 of 139

<sup>3 Note: Participants can be rescreened up to 2 times with the sponsor's medical director approval (refer to Section 4.2.4 of the CSP). For the determination of baseline all data reported will be used including data from previous screening periods.

#### 6.7.5.5. Patient Global Impression of Change scale (PGI-C) in Adults

PGI-C will be completed every 14 days. Adult participants enrolled under global CSP amendment 2 and later will complete the PGI-C on an electronic device where validated translations are available in the local language. Participants enrolled prior to global CSP amendment 2 will not complete the PGI-C.

The PGI-C assesses the change of overall status since the start of the study. The response options of the PGI-C are scored using a 7-point scale: 1 = Very Much Improved; 2 = Much Improved; 3 = Minimally Improved; 4 = No Change; 5 = Minimally Worse; 6 = Much Worse; 7 = Very Much Worse. Values less than 4 indicate an improvement, while values greater than 4 indicate worsening since start of the study.

No additional scoring will be performed for the PGI-C. If PGI-C was assessed more than once within 2 weeks, the observation closest to the target Study Day will be selected; or the latter observation if 2 observations are equally close to the target Study Day. All data will be listed.

#### 6.7.5.6. EQ-5D-5L

A sample of the EQ-5D-5L questionnaire is provided in Appendix F. The EQ-5D-5L questionnaire will be collected at Study Day 1, at Week 4, Week 16, Week 28, Week 40, Week 52 (EOT) and Week 56 (EOS). In case of assessments out of visit window, windowing will be applied as detailed in Section 6.5.

For calculation of the index score, the US value set will be used for all participants.

Baseline is defined as the most recent assessment on or before study day 1.

## 6.7.5.7. Quality of Life Questionnaire – Primary Ciliary Dyskinesia (QoL-PCD) for Adolescents

QoL-PCD has been added to ASPEN for adolescent participants in countries where translation is available (English, Spanish, Hebrew).

The QoL-PCD is separated as below:

- QoL-PCD for Adolescents (ages 13 to 17 years) includes 38 items divided into two sections, Section I: Quality of Life, and Section II. School, Work, or Daily Activities.
- QoL-PCD for Children (ages 6 to 12 years; questionnaire will be completed for participants at a year of 12 as inclusion into this study requires a minimum age of 12 years) includes 34 items.
- QoL-PCD for Parents / Caregivers (ages 6 to 12 years; questionnaire will be completed for participants at a year of 12 as inclusion into this study requires a minimum age of 12 years) includes 35 items divided into two sections, Section I: Quality of Life, and Section II. Symptoms.

The questionnaire has 9 subscales in the 13-17 years of age group: Physical Functioning (n=5), Vitality (n=3), Emotional Functioning (n=5), Treatment Burden (n=4), Upper Respiratory Symptoms (n=4), Lower Respiratory Symptoms (n=6), Role (n=4), Social Functioning (n=3), Hearing Symptoms (n=2).

CONFIDENTIAL Page 45 of 139

Scoring will be performed as indicated in Appendix B. The QoL-PCD will be collected at Study Day 1, at Week 4, Week 16, Week 28, Week 40, Week 52 (EOT) and Week 56 (EOS).

Baseline is defined as the most recent assessment on or before study day 1.

#### 6.7.5.8. Health care resource utilization

The derivation of hospitalizations per person-year will be done as described in Section 6.7.1.4. The eCRF "Doctor visits and ER visits YN" and the corresponding form "Doctor visits and ER visits log" will be used to calculate the number of outpatient and ER visits. The record for "Healthcare visit type" will differentiate between outpatient visit ("Doctor office visit", "Urgent care visit") and an ER visit ("Emergency room visit").

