# 2.3. Exploratory Objectives and Endpoints

The exploratory objectives and endpoints are presented in Table 3.

**Table 3:** Exploratory Objectives and Endpoints

Objective		Endpoint		
1.	To evaluate the effect of brensocatib compared with placebo on daily symptoms, as assessed by the average daily BEST score over the 52-week treatment period	Average daily change from Baseline in BEST score over the 52-week treatment period		
2.	To evaluate the effect of brensocatib compared with placebo on the average duration of PEs over the 52-week treatment period	Duration of adjudicated PEs over the 52-week treatment period		
3.	To evaluate the effect of brensocatib compared with placebo on the number of days of hospitalization due to PEs over the 52-week treatment period	Days hospitalized due to adjudicated PEs per patient year over the 52-week treatment period		
4.	To evaluate the effect of brensocatib compared with placebo on the number of days of absence from work (or number of days of school absence in case the subject is of school age) due to PEs over the 52-week treatment period	Days of absence from work/school due to adjudicated PEs per patient year over the 52-week treatment period		
5.	To evaluate the effect of brensocatib compared with placebo on lung function, as measured by change in pulmonary function parameters including prebronchodilator and postbronchodilator FEV 1 , FVC, PEFR, ppFEV 1 , and FEF(25-75%) over the 52-week treatment period	Change from Baseline in prebronchodilator and postbronchodilator FEV 1 , FVC, PEFR, ppFEV 1 , and FEF(25-75%) at Weeks 16, 28, 40, 52, and over 52 weeks		
6.	To evaluate the effect of brensocatib compared with placebo on health care resource utilization (outpatient visits, ER visits, hospitalization for any reason) over the 52-week treatment period	Outpatient visits, ER visits, and hospitalizations for any reason		
7.	To evaluate the effect of brensocatib compared with placebo on quality of life, as assessed by the age-appropriate QOL-PCD domain scores over the 52-week treatment period in adolescent subjects (≥12 to <18 years of age) with PCD	Change in QOL-PCD domain scores from Baseline to Weeks 16, 28, 40, 52, and Over 52 Weeks in adolescent subjects (≥12 to <18 years of age) with PCD		
8.	To evaluate the effect of brensocatib compared with placebo on quality of life, as	Change from Baseline in EQ-5D-5L score from Baseline to Week 52		

Objective	Endpoint

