#### 6.7.1.4. Days Hospitalized for Adjudicated PEs per Person-Year

Hospitalization for adjudicated PEs will be identified through the CRF "Hospitalization visits log" and the reason for hospitalization given as "Indication under study". The recorded admission and discharge dates will be used to calculate participants number of days hospitalized, e.g.,

$$duration(days) = date\ discharge-admission\ date+1.$$

For missing admission or discharge dates, the duration of hospitalization will not be calculated.

The number of days hospitalized due to adjudicated PEs per person-year is calculated as total number of days hospitalized due to indication under study by the total time on treatment:

$$(days\ hospitalized\ for\ indication\ under\ study\ per\ person\_year)_{trt} \\ = \frac{\sum (days\ hospitalized\ for\ indication\ under\ study)_{i,trt}}{\sum time\_on\_treatment_{i,trt}(years)},$$

where i describes the participant of  $trt \in \{\text{brensocatib 10mg, brensocatib 25mg or placebo}\}$ . The total time on treatment in days will be calculated for each treatment (trt) by pooling all patients time on treatment in years together.

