**Table 8: Exploratory Endpoints** 

Variable	Population Level Summary	Estimand Name	Treatment Regimen	ICEs/ Strategy	Section
Average Daily Change from Baseline in Bronchiectasis Exacerbation and Symptom Tool (BEST) score Over the 52-Week Treatment Period	Mean Difference	On-Study	Assignment to IP regardless of discontinuation or modifications to standard of care	Early discontinuation from randomized IP / Treatment Policy Modification to standard of care / Treatment Policy	8.5.1
Duration of exacerbation events that meet the protocol definition of PE diagnosis Over the 52- Week Treatment Period	Mean Difference	On-Study	Assignment to IP regardless of discontinuation or modifications to standard of care	Early discontinuation from randomized IP / Treatment Policy Modification to standard of care / Treatment Policy	8.5.2
Days Hospitalized for Adjudicated PEs per patient year Over the 52-Week Treatment Period	Mean Annualized Rate	On-IP	Randomized IP regardless of modifications to standard of care	Early discontinuation from randomized IP / While On-Treatment	8.5.3
Days of Absence from Work/School Related to Adjudicated PEs per Patient Year Over the 52-Week Treatment Period	Mean Annualized Rate	On-IP	Randomized IP regardless of modifications to standard of care	Early discontinuation from randomized IP / While On-Treatment	8.5.4

CONFIDENTIAL Page 65 of 139

Change from Baseline in prebronchodilator and postbronchodilator FEV 1 , forced vital capacity (FVC), peak expiratory flow rate (PEFR), percent predicted forced expiratory flow in 1 second (ppFEV 1 ) and forced expiratory flow between 25% and 75% of forced vital capacity (FEF [25-75%] ) at Weeks 16, 28, 40, and 52	Mean Difference	On-Study	Assignment to IP regardless of discontinuation or modifications to standard of care	Early discontinuation from randomized IP / Treatment Policy Modification to standard of care / Treatment Policy	8.5.5
Outpatient Visits, emergency room (ER) visits, and hospitalizations for any reason	Mean Annualized Rate	On-IP	Randomized IP regardless of modifications to standard of care	Early discontinuation from randomized IP / While On-Treatment	8.5.6

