#### 8.5.6. Outpatient Visits, ER Visits, and Hospitalizations for any Reason

The outpatient visits, ER visits, and hospitalizations for any reason per patient year will be presented and will utilize the ITT Analysis Set (see Section 5.2). The derivation of the endpoint is detailed in Section 6.7.5.8.

The number of outpatient visits, ER visits, duration of hospitalization in days, and hospitalizations for any reason per patient year will be summarized by treatment group using descriptive statistics.

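### The hospitalization part of the any-reason resource-use endpoint is derived with a rule restricted to stays for the indication under study

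*SAP*

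**What the plan says.** The endpoint is named in three places, and all three make it all-cause. Protocol 2.3, Table 3, item 6 lists "Outpatient visits, ER visits, and hospitalizations for any reason". SAP Table 8 repeats it as "Outpatient Visits, emergency room (ER) visits, and hospitalizations for any reason", with a mean annualized rate under the On-IP estimand. SAP 8.5.6 plans the output: "hospitalizations for any reason per patient year will be summarized by treatment group using descriptive statistics". It lists the duration of hospitalization in days as a separate item.

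For the definition, SAP 8.5.6 says "The derivation of the endpoint is detailed in Section 6.7.5.8". Section 6.7.5.8 treats the components differently. Outpatient and ER visits are taken from their own log and sorted by type of visit, with no condition on the reason. Hospitalizations get one sentence: "The derivation of hospitalizations per person-year will be done as described in Section 6.7.1.4".

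Section 6.7.1.4 is headed as hospital days for adjudicated exacerbations. It selects entries from the hospitalization log with "the reason for hospitalization given as 'Indication under study" (the form category for the disease itself). It sums the days of those stays and divides by total time on treatment in the arm. It adds: "For missing admission or discharge dates, the duration of hospitalization will not be calculated".

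**The concern.** An all-cause admission measure exists to show whether fewer bronchiectasis admissions come with fewer admissions overall, or are offset by stays for other causes. If the disease filter carries over through the cross-reference, the table would bear an all-cause label but hold a disease-specific number. A reader of the study report could not tell the difference from the label.

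The plan itself expects relevant admissions outside the disease. Protocol 4.2.2.1 lists serious infection other than an exacerbation, including infection needing parenteral antibiotics and hospital admission, as a reason for stopping study drug. Protocol 9.10.3.3 makes severe infections events of special interest and keeps exacerbations out of that category. Stays of this kind are what the filter would remove.

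**Working it through.** No published figure has to be reproduced, so the check is a trace of cross-references followed by a little algebra.

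**Trace**

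| Step | Place | Content for hospitalizations |
|---|---|---|
| 1 | Protocol 2.3, Table 3, item 6 | All-cause |
| 2 | SAP Table 8 | All-cause, annualized, On-IP |
| 3 | SAP 8.5.6 | All-cause, per patient year, plus days; derivation sent to 6.7.5.8 |
| 4 | SAP 6.7.5.8 | Sent to 6.7.1.4, no modification stated |
| 5 | SAP 6.7.1.4 | Only stays for the indication under study; days divided by time on treatment |

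Steps 1 to 3 and step 5 cannot both describe the same quantity, and step 4 does nothing to reconcile them.

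**Is there another derivation?** No other SAP section derives all-cause stays. SAP 8.5.3, the exacerbation-hospitalization endpoint, also points to 6.7.1.4, and there the filter fits.

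**Is it a declared change?** SAP Section 1 says differences from the protocol are discussed in Section 13. Section 13 lists changes to several of the protocol 2.3 exploratory endpoints, some of wording only (for example PGI-C), and nothing on this one. The all-cause definition therefore still stands.

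**What the literal rule gives.** In one arm let N be all hospital days, D the days for the indication under study, and T total time on treatment.
- Required by 8.5.6: N / T.
- Given by 6.7.1.4: D / T, which is the 8.5.3 quantity.
- Shortfall: (N − D) / T, which is zero or positive because D cannot exceed N. As a share of the true rate it is 1 − D/N.

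**Effect on the comparison of arms.** Write s = D/N for each arm. Then filtered ratio = true ratio × (s on brensocatib / s on placebo). The rate in each arm can only be understated. The ratio is unchanged if the shares are equal and moves in either direction if they differ. The documents give neither D nor N, so neither the size of the shortfall nor the direction of any distortion between arms can be computed.

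**Count of stays.** SAP 8.5.6 asks for days and for hospitalizations per patient year as separate items. Section 6.7.1.4 has a formula for days only, so the number of stays has no derivation at all.

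**The case against.** The strongest reply is that the cross-reference can be read narrowly. Section 6.7.1.4 is plainly written for exacerbations, and the sentence in 6.7.5.8 speaks of hospitalizations per person-year. It may therefore mean to borrow only the log, the date arithmetic and the person-time formula. The endpoint's name in three places supports that intent, and the literal reading makes the hospital-days result duplicate 8.5.3. This is probably what was meant. It is not what is written: 6.7.5.8 does not lift the filter, and in 6.7.1.4 the restriction sits in both the record selection and the formula's numerator.

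A second reply is that counting log entries needs little definition. That largely stands, and the missing count rule alone would be a small matter.

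Three stronger readings should be resisted.

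- A reader might infer that all-cause hospitalization is never measured. The documents do not support this. Protocol 3.1 and the health-resource footnote to Protocol Table 5 collect each healthcare visit with its type and reason, and SAP 8.5.6 still commits to the summary.
- A reader might infer that a rise in other admissions would be hidden. Inpatient hospitalization is a seriousness criterion (Protocol 9.10.2). Serious treatment-emergent events are tabulated by arm, organ class and preferred term (SAP 9.2), and events of special interest have their own tables with risk differences against placebo (SAP 9.3). These do not give an all-cause admission rate, but such a rise would be visible there.
- A reader might infer that stays with a missing date drop out of the count. Section 6.7.1.4 says only that their duration is not calculated. Whether to impute an end date for an open stay is a matter of preference, and the documents do not require it.

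**Conclusion.** The point holds as an error in a derivation rule. As written, the hospitalization part of the any-reason endpoint is restricted to the indication under study. That contradicts the protocol, SAP Table 8 and SAP 8.5.6, and it duplicates 8.5.3. The number of stays is not derived.

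The understatement in each arm equals the share of hospital days not attributed to the disease, which the documents do not give. No direction of bias between arms can be claimed without an assumption about how that share differs by arm.

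The consequence is limited. This is one component of one exploratory endpoint, summarized descriptively with no model or test, and it lies outside the 12 hypotheses in the multiplicity procedure of SAP 6.3. Primary and secondary conclusions and the power calculation are untouched. The conclusion rests on reading 6.7.5.8 as it stands; if programming already ignores the filter, the text is still wrong and should match.

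**What to change.** Replace the hospitalization sentence in SAP 6.7.5.8 with a rule that says:

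- all records in the hospitalization log are used, whatever the recorded reason;
- the number of hospitalizations is the count of admissions in the On-IP period;
- days are computed from admission and discharge dates;
- Section 6.7.1.4 is cited only for the date arithmetic and the person-time denominator.

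Sections 6.7.1.4 and 8.5.3 can stay as they are for the exacerbation endpoint. The cost is one paragraph of SAP text and the removal of one filter in programming, with no new data collection. It should be done before unblinding, because SAP Section 1 treats any analysis not described in the plan and run after unblinding as post hoc.

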# 6.7.5.9. Bronchiectasis Scoring Technique for Computed Tomography and Airway-Artery

Definitions of CT substudy endpoints will be described in a separate SAP.

#### 6.7.5.10. Completion Rates

Completion rates for PRO instruments will be calculated for each domain by timepoint and treatment group. Completion rates are presented as percentages as given below:

Completion\_Rate(%)domain,timepoint = 
$$\frac{\#instrument\_received}{\#instrument\_expected} * 100.$$

## 6.8. Definitions and Derivations of Pharmacodynamic Parameters

Pharmacodynamic parameters are NE, CatG, and PR3.

Sample collection schedules are listed in Appendix H.

#### **Derived activity parameters**

The percentage (%) change from baseline in PD parameters will be calculated as

$$PD_{param1}(\%) = (fold_{change} - 1) * 100$$

While the ratio between post-treatment and baseline results defines the fold change:

$$fold\_change = \frac{post\_treatment\ activity}{pre\_treatment\ activity}.$$

#### **Pre-treatment / Baseline**

The pre-treatment result is defined as the arithmetic mean of PD parameter results at screening and baseline.

#### Change from pre-treatment / Change from baseline

 $Change\ from\ pre\_treatment = post\_treatment - pre\_treatment\ .$ 

CONFIDENTIAL Page 46 of 139

#### **Maximum reduction**

The lowest post-treatment change from baseline result will identify the maximum reduction for the respective participant.

#### Time to maximum reduction

The time to maximum reduction in days will be calculated by participant and parameter as

Time to maximum reduction (days) = date of maximum reduction - date of first IP administration + 1.

## 6.9. Handling of Missing Data

The handling of missing data and appropriate imputations are described in the following sections and will be performed after all efforts fail to obtain the data.

### 6.9.1. Missing PRO Administrations and Missing Item Responses

Missing individual item PRO responses will not be imputed.

Domain scores will be calculated as per corresponding PRO manual, the derivations are described within corresponding variable section. In case the domain score is not evaluable, it will be treated as missing and will follow the rules specified for missing data handling described within the corresponding efficacy section.

#### 6.9.2. Missing Start and Stop Dates for Prior and Concomitant Medication

The rules to categorize medications to 'Prior' or 'Concomitant' are described in Section 6.4.8. There is no need to impute missing or partially missing start or stop dates.

Special care will be taken for partially reported dates of antibiotic therapy when identifying ICEs:

#### **Incomplete Start Date**

In the case where only the day is missing, the following imputation rules will be applied:

- If the month and year are the same as the year and month of the first IP administration date, then the first IP administration date will be assigned to the missing day;
- If either the year of the partial date is before the year of the first IP administration date or the years of the partial date and the first IP administration date are the same, but the month of partial date is before the month of the first IP administration date, then the last day of the month will be assigned to the missing day;
- If either the year of the partial date is after the year of the first IP administration date or the years of the partial date and the first IP administration date are the same, but the month of partial date is after the month of the first IP administration date, then the first day of the month will be assigned to the missing day;
- If the stop date is not missing, and the imputed start date is after the stop date, the start date will be imputed by the stop date.

CONFIDENTIAL Page 47 of 139

In the case where both day and month are missing, the following imputation rules will be applied:

- If the year is the same as the year of the first IP administration date, then the day and month of the first IP administration date will be assigned to the missing fields;
- If the year is prior to the year of the first IP administration date, then December 31 will be assigned to the missing fields;
- If the year is after the year of the first IP administration date, then January 1 will be assigned to the missing fields.

In the case where day, month and year are missing, the therapy will be considered as ongoing throughout participant's study participation.

